**POST MARKETING SURVEILLANCE (NON-INTERVENTIONAL STUDY)
FOR EVALUATING THE EFFICACY AND SAFETY OF DYSPORT CZECH
PATIENTS SUFFERING FROM POST-STROKE ARM SPASTICITY**

STUDY PROTOCOL

Study number: A-38-52120-113-PMS

PRODUCT NAME: Dysport

Final Version 4.0 dated: 13th February 2012

**Sponsor's Medically Responsible
Person: :**

[name]
Ipsen Pharma, o.s.
[name]
Czech Republic
Tel: PPD [REDACTED]
Fax: PPD [REDACTED]

Sponsor's Co-ordinating Office:

Ipsen Pharma, o.s.
[name]
Czech Republic
Tel: PPD [REDACTED]
Fax: PPD [REDACTED]

Monitoring Office:

Ipsen Pharma
[name]
[name]
Czech Republic
Tel: PPD [REDACTED]
Fax: PPD [REDACTED]

Co-ordinating Investigator:

Ass. [name]. [name]
Head of Neurological Department
Krajská Nemocnice Pardubice
[name],
[name]
Czech Republic
Tel: PPD [REDACTED]
Fax: PPD [REDACTED]

Pharmacovigilance/Emergency contact

PPD [REDACTED]
Ipsen Pharma, o.s.
[name]
Czech Republic
Tel (mobil): PPD [REDACTED]
Fax: PPD [REDACTED]

PROTOCOL SIGNATURES**Investigator Signature:**

I have read and agree to the **A POST MARKETING SURVEILLANCE (NON-INTERVENTIONAL STUDY) FOR EVALUATING THE EFFICACY AND SAFETY OF DYSPORT CZECH PATIENTS SUFFERING FROM POST-STROKE ARM SPASTICITY**. I am aware of my responsibilities as an Investigator under the guidelines of Good Clinical Practice (GCP)¹, local regulations (as applicable) and the Study protocol. I agree to conduct the study according to these guidelines and to appropriately direct and assist the staff under my control, who will be involved in the Study.

NAME:

TITLE:

PRINCIPAL INVESTIGATOR:

SIGNATURE: _____

DATE: _____

OFFICE:

Full investigational site contact details, including telephone numbers, will be documented in the Trial Master File.

On behalf of the Sponsor:

NAME:

[name]

TITLE:

Medical Director

SIGNATURE: _____

DATE: _____

OFFICE:

Ipsen Pharma, Prague

¹ ICH Harmonised Tripartite Guideline E6: Note for Guidance on Good Clinical Practice (CPMP/ICH/135/95) Step 5, adopted by CPMP July 1996.

SYNOPSIS

Study Title:	A post marketing surveillance (non-interventional study) for evaluating the efficacy and safety of Dysport Czech patients suffering from Post-Stroke Arm Spasticity
Study Objectives:	To provide a further assessment of the risk/benefit of Dysport as a marketed product
Phase of Study:	Post Marketing Study (non-interventional study)
Study Design:	Centres will prescribe Dysport according to their usual practice and within the latest approved Summary of Product Characteristics (SmPC). (Last approved version dated 30.06.2008, ref.nr.6324/2007;24731/2008;35386/2008). Each center will record the treated muscles and the dose of Dysport administered. At visits during following year (5 visits assumed) prescriber will evaluate treatment success and administration interval and fulfil simple Case Record Form (CRF). Based on the subject interview, the prescriber will fulfil the DAS QOL questionnaire and in case of related AE, the AE reporting forms. Both will be returned to Ipsen.
Study duration	“Recruitment” period will be 18 months. Duration of Study is approximately one year per subject (three injections expected within 1 year according to SmPC)
Study Population:	Reports on up to 200 male or female adult subjects will be collected. Study Inclusion Criteria All subjects must fulfil the following: 
 • Subjects with stroke either haemorrhagical or ischemic origin and stroke onset at least 3 months prior to study entry scheduled to receive Dysport. • Adults over the age of 18 years • Arm spasticity with Modified Ashworth scale ≥ 2 at least in one part Study Exclusion Criteria Subjects presenting with any of the following will not be included in the Study: 
 • Hypersensitivity to any Dysport ingredient • Pregnancy • Previous administration of botulinum toxin

Study Treatment:	
Investigational Medicinal Product (IMP):
 
Dysport, botulinum toxin A, presented in a form of lyophilizate injections is used for several indications including post stroke arm spasticity of adults. The pack contains 1 or 2 glass vials with lyophilizate and should be reconstituted with 0,9 % NaCl before administration.
 
The dosage will be set by physician according to SmPC. The maximal dose will be 1000 U per session.

Study Evaluations:	
Primary Efficacy Endpoint and Evaluation:
 
Global assessment of spasticity (Modified Ashworth scale)
 
Secondary Efficacy Endpoints and Evaluations:
 
Patient´s Quality of Life (QOL) evaluation (DAS scale)
 
Interval between separate administration sessions
 
Safety Endpoints and Evaluations:
 
Monitoring of treatment related adverse events (RAEs).
 
Pharmacokinetic Endpoints and Evaluations:
 
None
 
Pharmacodynamic Endpoints and Evaluations:
 
None

Statistical Methods:	
In terms of study reporting, the statistical analysis will be only descriptive: data summaries will consist of summary statistics like counts, mean, standard deviations, medians, minima, maxima or frequencies / percentages as appropriate. ITT / safety population will be used to describe all efficacy data and safety data.

TABLE OF CONTENTS

SIGNATURE PAGE	2
SYNOPSIS	3
Study Inclusion Criteria	3
Study Exclusion Criteria	3
1. LIST OF ABBREVIATIONS AND DEFINITION OF TERMS	8
2. INTRODUCTION	9
2.1 Disease Review	9
2.2 Compound Review	9
2.3 Clinical Study Rationale	9
3. STUDY OBJECTIVES	9
3.1 Primary Study Objective	9
3.2 Secondary Study Objectives	9
4. STUDY DESIGN	9
4.1 Overview	9
4.1.1 Population Characteristics	10
4.1.2 Design	10
4.2 Endpoints	10
4.2.1 Efficacy Endpoints	10
4.2.2 Safety Endpoints	10
4.3 Justification of Design	10
4.3.1 Study Duration	10
5. COMPLIANCE WITH GOOD CLINICAL PRACTICE, ETHICAL CONSIDERATIONS & INFORMED CONSENT	11
5.1 Compliance with Good Clinical Practice and Ethical Considerations	11
5.2 Informed Consent	11
6. STUDY POPULATION	12
6.1 Subject Identification Code List and Number of Subjects	12
6.2 Inclusion Criteria	12
6.3 Exclusion Criteria	12
6.4 Discontinuation /Withdrawal Procedures	12
7. METHODOLOGY	12
7.1 STUDY Schedule	12
7.2 Study Visits	13
7.2.1 Baseline (Day 1, visit V1)	13
7.2.2 Follow-up visits (V2, V3, V4, V5)	14
7.2.3 Study Completion or Withdrawal	14
8. STUDY EVALUATIONS	14
8.1 Efficacy Endpoints and Evaluations	14
8.1.1 Primary Efficacy Endpoint and Evaluations	14

8.1.2 *Secondary Efficacy Endpoints and Evaluations* 14

8.2 **Safety Endpoints and Evaluations**..... 15

8.2.1 *Related Adverse Events* 15

9. **STUDY TREATMENTS** 15

9.1 **Study Treatments Administered** 15

9.2 **Subject Identification and Allocation to Study Treatment** 15

9.3 **Study Treatment Supply**..... 16

9.4 **Compliance**..... 16

9.5 **Study Treatment Storage**..... 16

1. LIST OF ABBREVIATIONS AND DEFINITION OF TERMS

RAE	Related Adverse Event
CA	Competent Authorities
CDDS	Clinical Development Data Sciences (relates to Sponsor)
CRF	Case Report Form
CRO	Contract Research Organisation
DAS	Disability Assessment Scale
EU	European Union
GCP	Good Clinical Practice
ICH	International Conference on Harmonisation
IEC	Independent Ethics Committee
STUDY medication	Investigational Medicinal Product synonymous with “study drug”
IRB	Institutional Review Board
ITT	Intention to Treat
MedDRA	Medical Dictionary for Regulatory Activities
QOL	Quality of Life
RAP	Reporting and Analysis Plan
SAE	Serious Adverse Event/Experience
SAS[®]	Statistical Analysis System [®]
SmPC	Summary of Product Characteristics
SOP	Standard Operating Procedure
SUSAR	Suspected Unexpected Serious Adverse Reactions
TFLs	Tables, Figures and Listings
TEAE	Treatment Emergent Adverse Event
TMF	Trial Master File
AIFP	Association of Innovative Pharmaceutical Industry
SUKL	State Institute for Drug Control

2. INTRODUCTION

2.1 Disease Review

Not Applicable (N/A)

2.2 Compound Review

Dysport is the formulation of *Clostridium botulinum* type A toxin-hemagglutinin complex manufactured by Ipsen. It is currently available commercially in over 60 countries. It is registered for the treatment of blepharospasm, hemifacial spasm, cervical dystonia, post stroke arm spasticity, post stroke leg spasticity, cerebral palsy equinus foot spasticity, hyperhidrosis and glabellar wrinkles although not all indications are approved in all countries.

2.3 Clinical Study Rationale

Non-interventional studies include the continuous evaluation that takes place after regulatory approval, when the drug is already on the market and available for general use. These studies are designed to monitor effects of selected medical treatments in routine use without direct influence on standard clinical practice.

The intention of this non-interventional study is to collect safety data, efficacy data, treatment interval and quality of life based on routine treatment of subjects with Post-Stroke Arm Spasticity.

3. STUDY OBJECTIVES

3.1 Primary Study Objective

To provide a further assessment of the risk / benefit of Dysport as a marketed product.

3.2 Secondary Study Objectives

To provide quality of life assessment and to gather exploratory data on the interval between treatment injections.

4. STUDY DESIGN

4.1 Overview

Centres will prescribe Dysport according to their usual practice and within the Summary of Product Characteristics (SmPC). Latest approved version ref.nr. 6324/2007,24731/2008,35386/2008 is dated 30.06.2008. Each center will record the treated muscles and the dose of Dysport administered. Before the first administration and 4 weeks after that, prescriber will evaluate treatment success and will assess quality of life in the range of routine practice (if available). According to SmPC, 3 Dysport injections are expected within 1 year. During all visits performed

within a year, simple Case Record Form (CRF) will be fulfilled. In case of treatment related AE, the AE reporting forms will be fulfilled. Both will be returned to Ipsen.

4.1.1 Population Characteristics

Adult subjects with Post-Stroke Arm Spasticity newly scheduled to receive Dysport, with stroke onset at least 3 months prior to study entry, within each participating centre are to be included in this Study. All subjects should rehabilitate under professional inspection at the same time.

A total of 200 subjects are expected to be recruited.

4.1.2 Design

This is an open, non-randomised, multi-centre, non-interventional, post-marketing study.

Subject will be asked to provide a written informed consent. Inclusion & exclusion criteria will be checked prior to study enrolment.

Modified Ashworth scale and DAS scale will be evaluated before the first Dysport injection and 4 weeks after it, if available according to routine practice.

During one year, investigator will count-up real administration interval between treatment injections.

4.2 Endpoints

4.2.1 Efficacy Endpoints

Primary Efficacy Endpoint and Evaluation:

- Global assessment of spasticity (Modified Ashworth scale)

Secondary Efficacy Endpoints and Evaluations:

- Patient's Quality of Life (QOL) evaluation (DAS scale)

- Interval between separate administration sessions

4.2.2 Safety Endpoints

Collection of treatment related adverse events.

4.3 Justification of Design

The aim of the Study is to provide additional risk / benefit information on the use of Dysport within the specifications of the SmPC. The Study is therefore non-interventional, and is designed only to collect data that would normally be available in the standard treatment of patients with Dysport within licensed indication. As such, no additional measures of efficacy or safety are being collected other than those recorded in normal practice.

4.3.1 Study Duration

“Recruitment” period will be 18 months.

Duration of Study is approximately one year per subject (according to SmPC, 3 injections are expected within 1 year)

The Study will be considered to have started at first subject inclusion. It will be considered to have finished after the last visit(V5) performed by telephone contact.

5. COMPLIANCE WITH GOOD CLINICAL PRACTICE, ETHICAL CONSIDERATIONS & INFORMED CONSENT

5.1 Compliance with Good Clinical Practice and Ethical Considerations

This Study must be conducted in compliance with GCP, the Declaration of Helsinki and International Conference on Harmonisation (ICH)*, the Ipsen Ethical code, the Ethical Code of AIFP** and will be submitted to database of non-interventional studies in the SÚKL***. The Study will be submitted to Multicenter Ethical Committee.

In addition, this Study will adhere to all local regulatory requirements.

5.2 Informed Consent

Subject will be asked to sign simple informed consent.

Prior to study entry, the Investigator, or a person designated by the Investigator, will explain the nature, purpose of participation in this non-interventional study to each subject, subject's legally acceptable representative or impartial witness. Written informed consent must be obtained prior to the subject entering the study (before initiation of any study-related procedure and administration of the study drug). Sufficient time will be allowed to discuss any questions raised by the subject.

The Sponsor will provide a sample informed consent form. The final version must contain all elements included in the sample form, in language readily understood by the subject. Each subject's original consent form, personally signed and dated by the subject or by the subject's legally acceptable representative, and by the person who conducted the informed consent discussion, will be retained by the Investigator. The Investigator will supply all enrolled subjects with a copy of their signed informed consent.

The consent form may need to be revised during the trial should important new information become available that may be relevant to the safety of the subject or as a result of protocol amendments. It is the Investigator's responsibility to ensure that all subjects subsequently entered into the study and those currently in the study sign the amended form. This is documented in the same way as previously described. Subjects who have completed the study should be informed of any new information that may impact on their welfare/wellbeing.

* International Conference on Harmonisation (ICH) E9 and Federal register Vol 63, No. 179 (September 1998)

** Association of Innovative Pharmaceutical Industry (Asociace inovativního farmaceutického průmyslu)

*** State Institute for Drug Control (Státní Ústav pro Kontrolu Léčiv)

6. STUDY POPULATION

6.1 Subject Identification Code List and Number of Subjects

Each Investigator will maintain a record of all subjects enrolled into the Study.

This record called Subject Identification Code List should be kept confidential at the Study centre and should contain the centre number, subject number, subject name, subject initials, and telephone number.

It is planned to recruit approximately 200 subjects in approximately 10-30 centres in Czech Republic.

6.2 Inclusion Criteria

All subjects must fulfil the following:

- 1) Subjects with stroke of either haemorrhagic or ischemic origin scheduled to receive Dysport, with stroke onset at least 3 months prior to study entry
- 2) Adults over the age of 18 years
- 3) Arm spasticity with Modified Ashworth scale ≥ 2 at least in one part

6.3 Exclusion Criteria

Subjects will not be included in the Study if :

- 1) Subject has hypersensitivity to Dysport (any of its components) or drugs with a similar chemical structure.
- 2) Subject is pregnant. Absence of pregnancy should be confirmed prior injecting the product.
- 3) Subject has been previously treated with any botulinum toxin.

6.4 Discontinuation /Withdrawal Procedures

Discontinuation of withdrawal should be recorded including the reason, if known

7. METHODOLOGY

7.1 STUDY Schedule

The schedule of observations and assessments during the Study are summarised below.

Table 1. Schedule of Observations

	V1 (D1)	V2 (approx. D28)	V 3	V 4	V5 - phone contact approx 3-5 weeks after V4
Demography& Eligibility	X				
Significant medical or surgical history	X				
Prior and concomitant medications	X				
Previous medication for stroke	X				
Treatment injections	X		X	X	
Related Adverse events	X	X	X	X	X
Modified Asworth assessment	X	X	Optional	Optional	X
DAS assessment	X	X	Optional	Optional	X
Interval assessment			X	X	

7.2 Study Visits

7.2.1 Baseline (Day 1, visit V1)

All subjects attending the centre for their normal Dysport treatment will receive Dysport as decided by the treating physician, in accordance with the SmPC. The following details will be recorded on the Study CRF:

- Centre number, Subject number, Subject initials
- Demography
- Significant medical or surgical history
- Prior and concomitant medication
- Previous medication for stroke
- Stroke details
- Modified Ashworth scale, DAS scale
- Dysport administration (location, dosage)
- Related Adverse Events (at this visit injection related AEs only)

7.2.2 *Follow-up visits (V2, V3, V4, V5)*

At the subject's scheduled return to the center (Visit 2, the date depends on investigator's judgement, it is usually about 4 weeks later), the investigator will make routine control of treatment efficacy (V2). During this visit, both Modified Ashworth and DAS scales are evaluated according to routine practice. Treating physician will also perform an assessment of safety, and details on any treatment related adverse events will be collected.

After fadeaway of Dysport effect, subject will come to next injection visits (V3, V4,) within which Dysport will be injected again according to investigator decision. Treatment interval will be counted (V3 - V1, V4 - V3).

Visit V5 will be performed by telephone contact and is also the End of study visit.

During visit 5, which will take place within 3-5 weeks following last injection, subjects will be contacted by telephone to discuss any treatment related Adverse events (RAEs) that they have had since their treatment and Modified Asworth and DAS scale.

Collection of treatment related adverse events, if any, will be made during V1, V2, V3, V4 and V5.

7.2.3 *Study Completion or Withdrawal*

Study is completed if current visits exceed 1 year from visit 1 or when the Dysport treatment is finished/withdrawn

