11.4 Statistical/Analytical Methods

Statistical analyses will be performed / managed by CRO.

A Reporting and Analysis plan (RAP) describing the planned statistical analysis in detail with tables, figures and listings (TFLs) templates will be developed as a separate document.

11.4.1 *Demographic and Other Baseline Characteristics*

Descriptive summary statistics (n, mean, standard deviation (SD), median, minimum, maximum) of demographic and treatment dosage/interval will be presented.

11.4.2 *Subject Disposition and Withdrawals*

The numbers of subjects who were treated, discontinued and completed at each of the Study periods will be tabulated. Primary reasons for discontinuation of Study treatment will be tabulated.

11.4.3 *Pharmacokinetic Data*

N/A

11.4.4 *Efficacy Evaluation*

Descriptive analyses will be provided using Modified Ashworth scale and DAS scale at each visit and describing also changes from visit 1.

11.4.5 *Safety Evaluation*

All safety data will be included in the subject data listings. Analyses and summary tables will be based upon the safety population.

RAEs will be coded according to the Medical Dictionary for Regulatory Activities (MedDRA) and will be classified by MedDRA preferred term and system organ class. RAE listings will be presented by subject, system organ class and preferred term.

Incidence of all reported RAEs/treatment emergent related AEs (TERAE) and SRAEs will be tabulated. In addition, summary tables will be presented by maximum intensity, drug relationship and RAEs/TERAEs associated with premature withdrawal of survey medication.

A TERAE is defined as any RAE that occurs during the active phase of the survey if:

- it was not present prior to receiving the first dose of Survey medication, or
- it was present prior to receiving the first dose of Survey medication but the intensity increased during the active phase of the survey, or
- it was present prior to receiving the first dose of Survey medication, the intensity is the same but the drug relationship became related during the active phase of the survey.

Treatment emergent RAEs will be flagged (*) in the RAEs listings.

Concomitant medication will be coded by using WHO Drug Dictionary and will be summarised with the number and percentage of subjects receiving concomitant medication by drug class and preferred drug name.

11.5 *Subgroup Analyses*

N/A

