 Appendix 3: SmPC of Dysport approved on 30.06.200829

17. REFERENCES

Brashear A. et al: Inter- and intrarater reliability of the Modified Ashworth Scale and the Disability Assessment Scale in patients with upper-limb poststroke spasticity. Arch Phys Med Rehabil. 2002 Oct;83(10):1349-54.

Ashworth B: Preliminary trial of carisoprodal in multiple sclerosis. Practitioner, 1964, 192: 540-2

Masur H: Symptomorientierte Skalen und Scores. Paresen. In: Skalen und Scores in der Neurologie. Quantifizierung neurologischer Defizite in Forschung und Praxis. 2nd ed. Stuttgart: Georg Thieme Verlag; 2000 p. 68-69

Modified Ashworth scale on affected upper limb – test on muscle spasticity

1) ELBOW FLEXORS	
No increase in muscle tone	 0
Slight increase in muscle tone giving a “catch” when the limb was moved in flexion or extension	 1
Slight increase in muscle tone, manifested by a catch, followed by minimal resistance throughout the remainder (less than half) of the range of movement (ROM)	 1+
More marked increase in muscle tone through most of the ROM , but limb was easily flexed	 2
Considerable increase in muscle tone – passive movements difficult	 3
Limb rigid in flexion or extension	 4
2) FOREARM PRONATORS	
No increase in muscle tone	 0
Slight increase in muscle tone giving a “catch” when the limb was moved in flexion or extension	 1
Slight increase in muscle tone, manifested by a catch, followed by minimal resistance throughout the remainder (less than half) of the range of movement (ROM)	 1+
More marked increase in muscle tone through most of the ROM, but limb was easily flexed	 2
Considerable increase in muscle tone – passive movements difficult	 3
Limb rigid in flexion or extension	 4

3) WRIST FLEXORS	
No increase in muscle tone	 0
Slight increase in muscle tone giving a “catch” when the limb was moved in flexion or extension	 1
Slight increase in muscle tone, manifested by a catch, followed by minimal resistance throughout the remainder (less than half) of the range of movement (ROM)	 1+
More marked increase in muscle tone through most of the ROM, but limb was easily flexed	 2

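### The primary endpoint, the Modified Ashworth scale, is scheduled at V5, but V5 is a telephone call and the scale can only be graded by moving the limb

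*Protocol*

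**What the plan says.** Section 4.2.1 of the protocol makes the Modified Ashworth scale the primary efficacy endpoint.

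Three places make V5 a telephone contact:

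- Table 1 in section 7.1 heads the column "V5 - phone contact approx 3-5 weeks after V4".
- Section 7.2.2 states: "Visit V5 will be performed by telephone contact and is also the End of study visit".
- Section 4.3.1 says of the study: "It will be considered to have finished after the last visit(V5) performed by telephone contact".

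The scale is nevertheless scheduled at V5. The row of Table 1 for V1 to V5 reads "Modified Asworth assessment X X Optional Optional X", and section 7.2.2 has subjects "contacted by telephone to discuss any treatment related Adverse events (RAEs) that they have had since their treatment and Modified Asworth and DAS scale".

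For the analysis, section 11.4.4 states: "Descriptive analyses will be provided using Modified Ashworth scale and DAS scale at each visit and describing also changes from visit 1". It makes no exception for V5.

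**The concern.** The scale in the appendix is a physical examination. Its grades depend on what is met "when the limb was moved in flexion or extension": a catch, resistance over part or most of the range of movement, difficulty with passive movement, or rigidity. Nobody can establish these over a telephone. A grade of 0, 1, 1+, 2, 3 or 4 recorded at V5 would be a patient's verbal impression written down as an examiner's finding, and the change from visit 1 would compare it with a hands-on baseline.

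What is at stake is the description of response after repeated injection. V5 falls 3 to 5 weeks after the last injection, close to the roughly 4 weeks between the first injection and V2. A reader of the report would naturally set V2 beside V5 to compare first and later response. That comparison would have no valid measurement on the V5 side.

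**Working it through.** The protocol states no power, significance level or effect size, so there is no planned figure to reproduce. The check sets the sections side by side and counts from Table 1.

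**1. Can the scale be graded at V5?**

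| Source | Content |
|---|---|
| Sections 4.3.1, 7.1 and 7.2.2 | V5 is a telephone contact |
| Table 1 and section 7.2.2 | Modified Ashworth scale scheduled at V5 |
| Appendix, Modified Ashworth form | Five muscle groups, each graded by resistance to movement of the limb |
| Whole protocol | No telephone or patient-reported version of the scale |

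The first and third rows make the second impossible to carry out as written. The DAS differs: section 8.1.2 has the investigator complete it from an interview with the subject, so a telephone DAS is feasible.

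**2. Which Modified Ashworth assessments does Table 1 schedule?**

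| Visit | Mode | Table 1 entry | Position in the injection cycle |
|---|---|---|---|
| V1 | In person | X | Before the first injection |
| V2 | In person | X | About 4 weeks after the first injection |
| V3 | In person | Optional | Return for re-injection, after the effect has faded |
| V4 | In person | Optional | Return for re-injection, after the effect has faded |
| V5 | Telephone | X | 3 to 5 weeks after the last injection |

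Post-baseline assessments marked X: V2 and V5, so 2. Of these by telephone: V5, so 1. The share that cannot be graded is 1/2 = 50% of the post-baseline visits marked X. This is a share of visit columns, not of the primary-endpoint information. After V2, the number marked X that can be graded is 0.

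**3. How many values are affected?**

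Item scores at V5 = subjects reaching V5 × muscle groups on the form. The form has 5 groups (elbow flexors, forearm pronators, wrist flexors, finger flexors, thumb flexors), and about 200 subjects are planned.

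- Upper bound, everyone reaches V5: 200 × 5 = 1,000.
- If half reach V5 (an assumption, for scale only): 100 × 5 = 500.
- Lower bound, every site leaves the V5 grades blank: 0 values recorded, and the column is empty.

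**4. Is V5 kept out of the analysis?**

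No. Section 11.4.4 covers each visit. Section 8 refers the reader to sections 7.1 and 7.2 for the timing of efficacy assessments, and both include the scale at V5. Section 4.1.2 names only the time before the first injection and 4 weeks after it, where routine practice provides the scale. It therefore disagrees with Table 1 about V5 but does not override it.

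**The case against.** Several points can be made for the protocol.

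- **The X may not be binding.** Section 4.1.2 ties the scale to routine practice, and section 4.3 says only measures recorded in normal practice are collected. Section 7.2.2 speaks of discussing the scale in the call, not of recording a grade. A site could leave V5 blank. This stands in part: invalid values are the likely result of following the schedule, not a certainty. But Table 1 separates X from optional and puts V5 with the X visits. Section 13.4 asks for reasons for missing data, section 13.5 has queries raised to resolve missing data, and section 14.4 pays per completed CRF. All of these push sites towards an entry. If the routine-practice wording does prevail, the protocol contradicts its own schedule and still needs correcting.
- **The main contrast is intact.** Sections 4.1 and 4.1.2 describe before the first injection against 4 weeks after it, and V1 and V2 are both in person. This stands fully.
- **The study is descriptive.** Section 11.3.1 excludes testing, and section 11.3 disclaims definitive conclusions about safety or efficacy. So no error rate, power or decision rule is touched. But description is all that the study delivers, and a misleading column for the primary endpoint damages exactly that.
- **The separate Reporting and Analysis Plan could drop V5.** It could, but it cannot make a telephone grade valid or correct the schedule that tells sites to collect one.

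**Conclusion.** The point holds and should be fixed. As written, the protocol schedules an examiner-graded primary endpoint at a visit with no examination and then summarises it as change from a hands-on baseline. One of the two post-baseline assessments marked X cannot be graded, and no gradable one marked X remains after V2. The number of item scores affected is at most 1,000. That ceiling assumes that all 200 subjects reach V5 and that all five groups are scored in each.

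The harm is confined to the V5 summary of the Modified Ashworth scale and to any statement about response after re-injection. The V1-to-V2 change, the DAS, the treatment intervals and the safety data are not affected by this defect. The conclusion rests on reading X in Table 1 as a scheduled assessment. On the weaker reading, that it applies only where routine practice provides it, the sections contradict each other and the V5 column is missing or mixed, with no rule to tell which.

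**What to change.** 1. In Table 1 (section 7.1), delete the Modified Ashworth entry at V5. Keep related adverse events and the DAS.
2. In the V5 paragraph of section 7.2.2, remove the Modified Ashworth scale from the content of the call.
3. In section 11.4.4, state that Modified Ashworth summaries and changes from visit 1 use in-person assessments only and exclude V5. Label the V5 DAS as obtained by telephone.
4. Align sections 4.1 and 4.1.2 with the corrected Table 1.
5. If a score after V4 is wanted, record it only when the subject is examined in person at a routine visit in that window. Report it on its own line with the number examined, not as V5. This keeps the study non-interventional.

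The cost is a wording amendment, with no added visits or staff. No valid data are lost. The amendment does not create a measurement after re-injection: unless some subjects are examined in person in that window, none is scheduled soon after a repeat injection. The report should then say that response on this scale is described for the first injection only.
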